2 SYNOPSIS

Study Title	Ketone supplementation to Improve Cardiac Energetics and Function	
Study Design	Single centre, prospective case control study.	
Study Participants Adult T2D patients, adult heart failure patients and healthy adults.		
Planned Sample Size	30 T2D patients 30 healthy individuals with no diabetes 30 adults with non-ischemic heart failure with systolic heart failure (ejection fraction <50%)	
Planned Study Period	07/08/2022 to 01/08/2025 for 36 months	
Primary Aim To advance our understanding of the physiological effects of myocardial energetic impairment, perfusion and cardiac contractile T2D and heart failure patients.		

Document: Research Protocol	
Short Title: KICK-Energy	Version 2.0
Chief Investigator: [name]	Date 09 Mar 2023
IRAS Project ID: 308642	Page 4 of 32

Objectives	Primary objective: Change in myocardial rest and dobutamine stress PCr/ATF	
	following 2 weeks of oral ketone ester supplementation (delta G three times daily).	
	Secondary objectives: Following oral ketone ester supplementation, changes in:	
	1) myocardial perfusion,	
	2) LVEF at rest; and during dobutamine stress;	
	3) Myocardial strain (systolic strain and diastolic strain rate).	
Primary Endpoint	Change in myocardial energetics during rest and dobutamine stress before and after oral ketone ester supplementation.	
Secondary Endpoints	Following oral ketone ester supplementation, changes in:	
	i) myocardial rest PCr/ATP,	
	ii) myocardial perfusion,	
	iii) left ventricular ejection fraction (LVEF) at rest;	
	iv) LVEF during dobutamine stress.	

Document: Research Protocol	
Short Title: KICK-Energy	Version 2.0
Chief Investigator: [name]	Date 09 Mar 2023
IRAS Project ID: 308642	Page 5 of 32

3 Abbreviations

AE Adverse event
AR Adverse reaction

ATP Adenosine triphosphate

CF Consent form
CI Chief Investigator
CRF Case Report Form

CMR Cardiac Magnetic Resonance scan (MRI scan of the heart)

CT Computed Tomography

DM Diabetes Mellitus

ECG Electrocardiogram

GCP Good Clinical Practice

GP General Practitioner

HbA1c Glycated hemoglobin

FA Fatty Acid

ICF Informed Consent Form

LV Left ventricle

MRS Magnetic resonance spectroscopy

MS Mass Spectroscopy

NHS National Health Service

PCr Phosphocreatine ³¹P-MR Phosphorus MR

PI Principal Investigator

PIL/S Participant/ Patient Information Leaflet/Sheet

R&I NHS Trust R&I Department
REC Research Ethics Committee
SAE Serious Adverse Event

SAE Serious Adverse Event
SAR Serious Adverse Reaction

SOP Standard Operating Procedure

SUSAR Suspected Unexpected Serious Adverse Reactions

T1D Type 1 diabetes
T2D Type 2 diabetes
TMF Trial Master File

TSC Trial Steering Committee

Document: Research Protocol	
Short Title: KICK-Energy	Version 2.0
Chief Investigator: [name]	Date 09 Mar 2023
IRAS Project ID: 308642	Page 6 of 32

Document: Research Protocol	
Short Title: KICK-Energy	Version 2.0
Chief Investigator: [name]	Date 09 Mar 2023
IRAS Project ID: 308642	Page 7 of 32

4 Introduction

4.1 Background

Heart failure and diabetes: Heart failure (HF) is the most common initial presentation of cardiovascular disease in diabetes¹⁻³. The risk of developing HF is increased 2.5-fold in patients with type 2 diabetes (T2D), and 1.7-fold in patients with prediabetes^{4, 5}. Once HF is established the risk of death increases 4- to 6-fold^{6, 7}, with fewer than one in five T2D patients with HF over the age of 65 surviving beyond five years⁸ – an outcome worse than for the most aggressive cancers. There is a clear and urgent need for better strategies to prevent the development of HF in T2D patients.

Energy metabolism in T2D: A major cause of cardiac dysfunction in T2D is impaired cardiac energy metabolism. The heart has a very high energy demand, while having minimal energy storing capacity⁹. Efficient matching of energy supply to demand in the heart is therefore essential for maintaining cardiac function. We have previously shown that cardiac energy levels are reduced in T2D patients and discovered that simple exercise activity exacerbates this energy starved state further¹⁰. Energy starvation in asymptomatic T2D patients preceded other abnormalities such as reductions in left ventricular (LV) ejection fraction or increase in LV mass ¹⁰⁻¹². These data suggest that myocardial energy metabolism offers both early diagnostic and therapeutic opportunities to prevent or modulate diabetic HF. Metabolic intervention strategies that modulate fuel uptake and utilization, or mitochondrial metabolism have already been proposed as therapeutic options^{13, 14}. However, the precise etiology of energy starvation and how the alterations of cardiac energy metabolism differ in the development of HF in T2D remain unknown. Such knowledge is critical for determining the most appropriate type of metabolic intervention in individual patients, in particular as some forms of metabolic intervention may be impractical, inefficient or potentially even harmful for some patient groups¹³.

Causes of myocardial energy deficiency in diabetes: Diabetes is a disorder of metabolic dysregulation. There are 3 key potential deleterious alterations in cardiac metabolism ultimately resulting in energy deficiency and impaired contractility in patients with T2D¹⁵: reduced myocardial blood supply^{10, 16}, loss of flexibility in myocardial fuel selection¹⁷ and impaired mitochondrial function¹⁸. There are also potentially beneficial metabolic alterations in the diabetic heart ameliorating this energy deficit such as enhanced ketone metabolism, which are a lot less researched but could be transformative for the prevention and treatment of heart disease in T2D.

Metabolic flexibility of the heart and the hierarchy of fuels in energy production efficiency: The healthy heart shows metabolic flexibility and consumes a wide range of energy fuels such as fatty acids (FAs), glucose, lactate, ketones, and some amino acids, to generate energy via mitochondrial oxidation^{19, 20}. The conservation of energy from the oxidation of these energy fuels is performed by the electron transport chain (ETC), where electrons from the redox reactions of fuel oxidation are trapped to create an electrochemical gradient across the inner-mitochondrial membrane to generate ATP. These fuels have different efficiencies in generating ATP and in their oxygen need during this process²¹. Consequently, altered cardiac metabolism may contribute to the development of cardiac dysfunction by affecting the myocardial oxygen demand and impairing the metabolic flexibility of the heart²¹. FAs yield more ATP per

Document: Research Protocol	
Short Title: KICK-Energy	Version 2.0
Chief Investigator: [name]	Date 09 Mar 2023
IRAS Project ID: 308642	Page 8 of 32

mol when oxidized than glucose^{22, 23}, but this is at a greater oxygen cost, with approximately 15% more oxygen per mol of ATP synthesized^{22, 24, 25}. An increased dependence on FAs relative to carbohydrates therefore decreases cardiac efficiency²⁶. Moreover, ketone oxidation yields more ATP per oxygen consumption than FA oxidation (as has been shown in the case of palmitate), ketones therefore representing a more energy-efficient fuel than FAs²⁷. Ketones are also more chemically reduced than pyruvate, and result in increased ETC redox span and greater ATP generation²⁸.

Ketosis: Friend or foe for the heart in patients with diabetes? The ketone bodies are generated by the liver from non-esterified FAs in response to energy depletion or starvation to maintain ATP generation in vital organs. By virtue of their evolutionary role, ketones conserve protein and carbohydrate stores, by substituting themselves as energy fuels²³. Ketosis was previously feared in type 1 diabetes, being associated with life-threatening acidosis. However, in a study of T2D patients presenting with hyperglycaemic crisis, those with ketosis (but not acidosis) had lower all-cause mortality than those without²⁹, suggesting that ketosis may potentially be protective in diabetes. Moreover, sodium–glucose-cotransporter-2 inhibitors(SGLT2i) which induce mild ketosis as a class effect, are associated with a lower risk of HF hospitalisation in T2D patients³⁰,³¹. The mild ketosis associated with SGLT2i is assumed to contribute to the cellular energy restoring effects of these drugs³²⁻³⁵. Because the energetic properties of ketones are favourable, increased myocardial ketone oxidation could mitigate myocardial energy starvation in diabetes and compensate for defects in mitochondrial energy generation^{27,36}.

Exogenous ketone ester: The ketone bodies, D-beta-hydro- xybutyrate (βHB) and acetoacetate, are not readily available in the human diet, but are produced in the liver from free fatty acids in response to low blood glucose and insulin levels, as an alternative to glucose as an energy supply for the brain. Until recently, blood ketones could only be raised over several days by fasting or by strictly following low-carb, high-fat diets. Similar blood βHB concentrations can now be attained within 30 min by drinking the ketone monoester, (R)-3-hydroxybutyl (R)-3-hydroxybutyrate, which introduces a new metabolic state, termed exogenous nutritional ketosis. Interventions that induce ketosis simultaneously lower blood glucose, as a result a recent study has assessed safety, tolerability, and effects of an exogenous ketone ester supplementation on glycaemic control in 21 patients with T2D ³⁷. The participants consumed 25 ml of ketone ester product 3 times daily for 4 weeks. This study assessed serum electrolytes, acid-base status, and beta hydroxybutyrate concentrations weekly and cardiovascular risk markers were measured before and after the intervention. The investigators have shown that exogenous ketosis using a ketone ester product was capable of inducing fasting-like elevations in serum β-hydroxybutyrate without the need for caloric or carbohydrate restriction. Importantly constant ketone ester consumption over 1 month was safe, well tolerated, and improved glycaemic control in patients with T2D. Safety of the same ketone ester product has also been shown in healthy volunteers³⁸. The only side effect detected in both studies was mild nausea.

While oral supplementation was not assessed in heart failure patients previously, another study assessed higher doses of ketone infusion in heart failure patients and demonstrated its safety³⁹

³¹Phosphorus Magnetic Resonance Spectroscopy and Myocardial Energetics Magnetic resonance spectroscopy (MRS) is the only noninvasive, non-radiation exposure technique for the investigation of

Document: Research Protocol	
Short Title: KICK-Energy	Version 2.0
Chief Investigator: [name]	Date 09 Mar 2023
IRAS Project ID: 308642	Page 9 of 32

cardiac metabolism *in vivo*, without the use of an external tracer. Maintenance of adequate levels of cardiac high-energy phosphate metabolites, ATP, the energy source for contraction, and phosphocreatine (PCr), the major energy storage compound, are of vital importance for normal heart function. The relative concentration of PCr to ATP (PCr/ATP) is a marker of the myocardium's ability to convert substrate into ATP for active processes, and a sensitive index of the energetic state of the myocardium⁴⁰. ³¹P-MRS yields peaks for PCr and the three phosphorus atoms of ATP, all of which are proportional to the cellular concentration of the metabolites. The primary energy reserve compound in the heart is PCr and the enzyme creatine kinase allows the transfer of the high-energy phosphate bond between ATP and PCr, through the phosphotransferase reactions, in order to diffuse energy from the mitochondria to the myofibrils as PCr⁴¹. The CK energy shuttle ensures thermodynamic control of the cell, maintaining a low concentration of free adenosine diphosphate near the mitochondria, and providing ATP to the myofibrils for muscle contraction. When demand for ATP outweighs ATP synthesis, PCr levels fall, resulting in a low PCr to ATP ratio. Decreased PCr/ATP ratio is a predictor of mortality⁴², linked to contractile dysfunction^{41, 42}, and is a recognized complication of diabetes^{43, 44}.

Cardiovascular Magnetic Resonance (CMR) and Myocardial Perfusion and Function CMR allows detailed characterization of the cardiac phenotype, and it is the reference standard technology for assessment of cardiac structural and functional changes. CMR is frequently utilised to determine disease pathophysiology, and it is the only imaging modality that can assess non-invasively cardiac function, ischaemia, perfusion and fibrosis¹¹. The latest technology for myocardial perfusion CMR allows fully automated analysis with perfusion values that are in close correlation with the reference standards of Positron Emission Tomography and microspheres⁴⁵.

4.2 Hypothesis

This study will test the hypothesis that ketones improve myocardial energetics and contractile function.

5 Objectives and Outcome Measures

Overall aim: This study aims to advance our understanding of the physiological effects of ketosis on myocardial energetic impairment, perfusion, and cardiac contractile function in T2D patients and in heart failure patients.

5.1 Primary Objectives:

Change in myocardial rest and dobutamine stress PCr/ATP after 2 weeks of oral ketone ester supplementation.

5.2 Secondary Objectives:

Document: Research Protocol	
Short Title: KICK-Energy	Version 2.0
Chief Investigator: [name]	Date 09 Mar 2023
IRAS Project ID: 308642	Page 10 of 32

Following 2 weeks of oral ketone ester supplementation, change in:

- 1) Myocardial perfusion,
- 2) LVEF at rest; and during dobutamine stress;
- 3) Myocardial strain (systolic strain and diastolic strain rate).

6 Study Design

Study design: Single centre, prospective case controls study.

Study duration: The study will run over 36 months. Each participant will remain in the study for a maximum of 4 weeks. We will schedule the second hospital visit (which is also the final hospital visit) within 2 week from the first hospital visit.

Setting: Leeds General Infirmary, University of Leeds

Study population: 30 T2D patients, 30 adults with systolic heart failure diagnosis, 30 healthy adults.

7 Study Participants

30 adult T2D patients and 30 adults with systolic heart failure diagnosis of non-ischemic etiology with LV ejection fraction <50% will be recruited. In addition, 30 healthy individuals will be recruited for the control group. Diabetes patients may receive any type of glucose lowering treatment or be treated with diet and exercise alone for at least 12 weeks prior to study.

7.1 Inclusion and Exclusion Criteria- T2D Participants

Inclusion criteria:

- 1) Men and women > 18 years of age;
- 2) 6.0≤HBA1c≤10% at screening;
- 3) Ability and willingness to provide written informed consent and to comply with the requirements of the study.

Exclusion criteria:

1) History of coronary artery disease, previous CABG, angioplasty or myocardial infarction;

Document: Research Protocol	
Short Title: KICK-Energy	Version 2.0
Chief Investigator: [name]	Date 09 Mar 2023
IRAS Project ID: 308642	Page 11 of 32

- 2) Known HF or reduced LVEF on baseline CMR (<50%);
- 3) Female participants who are pregnant, lactating or planning pregnancy during the course of the study;
- 4) Renal impairment (eGFR<30ml/min/m2);
- 5) Participation in a clinical trial in the preceding 12 weeks;
- 6) Contra-indications to CMR or to dobutamine or gadolinium;
- 7) Any type of diabetes other than T2D.

7.2 Inclusion and Exclusion Criteria- Healthy Volunteers

Inclusion criteria:

- 1) Men and women >18 years of age;
- 2) Mean HBA1c≤6%;
- 3) Ability and willingness to provide written informed consent and to comply with the requirements of the study.

Exclusion criteria:

- 1) Any type of diabetes;
- 2) Significant renal impairment (eGFR<30ml/min/m2);
- 3) Female participants who are pregnant, lactating or planning pregnancy during the course of the study;
- 4) Participation in a clinical trial of an investigational medicinal product in the preceding 12 weeks;
- 5) Contra-indications to MRI;
- 6) Known hypersensitivity to dobutamine or gadolinium;
- 7) History of coronary artery disease, previous CABG, angioplasty or myocardial infarction;
- 8) Known HF or reduced LVEF on baseline CMR (<50%).

7.3 Inclusion and Exclusion Criteria- Adults with Heart Failure with and without T2D

Inclusion criteria:

- 1) Men and women >18 years of age;
- 2) Ability and willingness to provide written informed consent and to comply with the requirements of the study;
- 3) Prior diagnosis of non-ischemic heart failure

Document: Research Protocol	
Short Title: KICK-Energy	Version 2.0
Chief Investigator: [name]	Date 09 Mar 2023
IRAS Project ID: 308642	Page 12 of 32

- 4) LV ejection fraction of <50% on prior CMR or echocardiography scans
 - 5) For participants with T2D: 6.0≤HBA1c≤10% at screening

Exclusion criteria:

- 1) Significant renal impairment (eGFR<30ml/min/m2);
- 2) Female participants who are pregnant, lactating or planning pregnancy during the course of the study;
- 3) Participation in a clinical trial of an investigational medicinal product in the preceding 12 weeks;
- 4) Contra-indications to MRI;
- 5) Known hypersensitivity to dobutamine or gadolinium;
- 6) History of coronary artery disease, previous CABG, angioplasty or myocardial infarction;
- 7) Any type of diabetes other than T2D.

7.4 Recruitment

There are 3 recruitment pathways in place:

- With assistance from the NIHR Yorkshire and Humber Clinical Research Network (CRN), the study team will recruit participants with T2D, healthy volunteers and heart failure patients (with or without T2D) from local GP practices. These practices will be provided the eligibility criteria for screening. They will also be provided the study protocol and the Participant Information Sheet (PIS). They will have detailed discussion about the study aims with the study investigators ([name] and her team). Potential participants will be identified from patient lists by a specialist nurse in the practice. Potential participants identified in this manner will be mailed an invitation letter with reply slip and a PIS by the practice. These forms will have the contact details for the study investigators. Participants who are willing to participate will this way be able to express their interest by directly contacting the investigators via mail, email or phone. The invitation letter will indicate that when this expression of interest has been received by the research team, the team will contact potential participants by telephone in the near future to answer any questions they may have about the study. If the potential participant is interested in participating, the research team will arrange a convenient time for the first study visit to take place.
- 2. The study team at the Leeds Teaching Hospitals NHS Trust (LTHT) will also contact those who have participated in previous observational ethically approved studies in the department (University of Leeds, Biomedical Imaging) and who have consented to have their contact details retained to be contacted if eligible to take part in other studies. We will consult the LTHT electronic patient record database (EPRO), Patient Pathway Manager (PPM) and/ or Patient Administration System (PAS)

Document: Research Protocol	
Short Title: KICK-Energy	Version 2.0
Chief Investigator: [name]	Date 09 Mar 2023
IRAS Project ID: 308642	Page 13 of 32

- containing up-to-date information regarding deceased patients prior to contacting in order to be contacted if eligible to take part in other studies.
- 3. The heart failure volunteers will be recruited by study team at LTHT from the previous ethically approved studies in the department and that have consented to be have their contact details to be retained to be contacted if eligible to take part in further studies. Heart failure patients may also be recruited from appropriate clinics at LTHT.

7.5 Informed Consent

Written and verbal versions of the Participant Information Sheet (PIS) and Informed Consent Form (ICF) will be presented to the participants detailing no less than: the exact nature of the study; what it will involve for the participant; the implications and constraints of the protocol; the known side effects and any risks involved in taking part. It will be clearly stated that the participant is free to withdraw from the trial at any time for any reason without prejudice to future care, without affecting their legal rights and with no obligation to give the reason for withdrawal.

The participant will be allowed as much time as they wish to consider the information, and the opportunity to discuss with the Investigator, their GP or other independent parties to decide whether they will participate in the trial. Written informed consent will then be obtained by means of dated participant signature and dated signature of the person who presented and obtained the informed consent on the ICF. The person who obtained the consent must be suitably qualified and experienced, and have been authorised to do so by the Chief/Principal Investigator. A copy of the signed ICF will be given to the participant. The original signed and dated form will be retained at the trial site.

The participant must personally sign and date the latest approved version of the Informed Consent form before any trial specific procedures are performed.

8 Methodology

8.1 Study Visits

[figure not shown]
The assessments listed below will be carried out at each visit in the Advanced Imaging Centre at the Leeds General Infirmary. All participants, including the ones with T2D and heart failure, will continue taking their previously prescribed medications throughout the study.

Participants will be asked to attend 2 hospital visits. To minimise the inconvenience of hospital visits we will arrange transport. The first study visit will take up to 2.5 hours and the second visit will take up to 2.5 hours as well but 2 weeks later following adequate oral ketone loading. Participants will not need to fast for the visits.

[figure not shown]
Asymptomatic T2D patients with no history of heart disease, non- ischemic heart failure patients with LV ejection fraction <50% and healthy controls will undergo ³¹P-MRS and CMR scans over two visits (see study

Document: Research Protocol	
Short Title: KICK-Energy	Version 2.0
Chief Investigator: [name]	Date 09 Mar 2023
IRAS Project ID: 308642	Page 14 of 32

flowchart below).

Visit 1: All participants will undergo CMR and ³¹P-MRS studies at 3.0Tesla for evaluation of rest and dobutamine stress myocardial energetics, perfusion and function (see scan protocol below). In order to study the impact of ketosis on the myocardial energetic response to acute increases in cardiac workload, MR experiments will be conducted at rest and during haemodynamic stress (dobutamine stress). Blood samples will be obtained for measuring the levels of plasma beta-hydroxybutyrate, acetoacetate, and glucose.

Visit 2: ³¹P-MRS and CMR studies will be repeated after oral ketone supplementation to assess the impact of ketosis on myocardial energy metabolism, perfusion and function.

The blood ketone level will be assessed and recorded on arrival. Ketosis will then be achieved via oral supplementation with ketone ester product Delta- G (BHB, TAS* Ltd), for 2 weeks three times daily between the 2 study visits. This product has been developed for commercial use by a University of Oxford spinoff company, TAS* Ltd and is available for use over the counter. The kinetics, safety and tolerability study of this product in healthy adults and in T2D patients suggested favourable results apart from mild gastrointestinal upset at higher doses^{37, 38}. While oral supplementation was not assessed in heart failure patients previously, another study assessed higher doses of ketone infusion in heart failure patients and demonstrated its safety³⁹.

Document: Research Protocol	
Short Title: KICK-Energy	Version 2.0
Chief Investigator: [name]	Date 09 Mar 2023
IRAS Project ID: 308642	Page 15 of 32

Baseline Assessments/Visit 1:

- Review of medical history and concomitant medications
- Review of history of diabetes and complications
- Review of inclusion/exclusion criteria
- Collection of demographic data (sex, ethnicity, age)
- Urine pregnancy test in women of childbearing potential
- Written informed consent
- Height, weight, waist, and hip circumferences
- 12-lead ECG
- Resting heart rate and blood pressure
- Venepuncture: 20mls of blood sample will be taken while inserting 2 venous lines (one
 line for dobutamine infusion and the other one for MRI contrast injection). This sample
 will be used for assessing blood ketone and glucose levels
- Multiparametric MRI
- Distribute 2 weeks supply of 25ml three times daily oral ketone ester product (Delta- G) supplementation
- Issue diaries and ketone finger prick test kits. The investigators will demonstrate how to
 perform the finger prick tests during this visit. In addition, the investigators will discuss
 how to keep the diary and answer any questions participants may have with regards to
 these tasks.

Study Visits:

Visit 2:

- 12-lead ECG
- Resting heart rate and blood pressure
- Venepuncture: 20mls and 2 venous lines (one line for dobutamine infusion and the other for MRI contrast injection).
- Small blood sample will be taken assess blood ketone and glucose levels
- Multiparametric MRI
- Collect and review diaries

End of the study.

Participants will be asked to self-administer a ketone finger prick test once a week at home while taking the ketone ester drink. They will be instructed to do this 1 week after starting

Document: Research Protocol	
Short Title: KICK-Energy	Version 2.0
Chief Investigator: [name]	Date 09 Mar 2023
IRAS Project ID: 308642	Page 16 of 32

the drinks, taking a reading immediately before and 30 minutes following the third drink on their least active day.

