8.2 Study Assessments

8.2.1 Blood Tests and Urine Pregnancy Test

Blood will be taken via venipuncture at visit 1 and visit 2. At Visits 1 and 2, the levels of plasma lipids, insulin, beta-hydroxybutyrate, acetoacetate, and glucose will be measured. At Visit 1, U&Es and HbA1c will also be measured. These blood tests are purely for research purposes. No additional interventions should be needed due to the results and participants will adhere to their usual treatment plans (if applicable).

Participants will be administered a urine pregnancy test at their first study visit (if applicable).

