Appendix C: Amendment History

Amendment No.	Protocol Version No.	Date is	ssued	Author(s) changes) of	Details of	f Changes	made		
1	2.0	09	Mar	[name]	Addition	of U&E,	HbA1c,	lipid	and
		2023		and [name]		insulin testing.				

Document: Research Protocol				
Short Title: KICK-Energy	Version 2.0			
Chief Investigator: [name]	Date 09 Mar 2023			
IRAS Project ID: 308642	Page 32 of 32

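### The paired scans are unfasted and not matched within person on meal state or time of day, which adds avoidable variance to the change being tested

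*Protocol*

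**What the plan says.** Section 8.1 (Study Visits) sets one rule on meal state for both visits: "Participants will not need to fast for the visits". On the timing of the second scan it says only that "the second visit will take up to 2.5 hours as well but 2 weeks later following adequate oral ketone loading". The Visit 2 "studies will be repeated after oral ketone supplementation to assess the impact of ketosis on myocardial energy metabolism, perfusion and function". The assessment lists for the two visits in the same section contain no entry for time of day, time of the last meal or time of the last ketone drink.

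Section 8.2.1 adds the blood sampling: "At Visits 1 and 2, the levels of plasma lipids, insulin, beta-hydroxybutyrate, acetoacetate, and glucose will be measured". The log in Appendix C gives the version 2.0 additions as U&E, HbA1c, lipid and "insulin testing". Glucose is not among them.

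Section 4.1 supplies the physiological premise. It says "The healthy heart shows metabolic flexibility and consumes a wide range of energy fuels", and that ketone bodies "are produced in the liver from free fatty acids in response to low blood glucose and insulin levels". It also says "Interventions that induce ketosis simultaneously lower blood glucose".

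Section 10 plans two-tailed paired t-tests and sizes the study for a rise of 0.18 in dobutamine stress PCr/ATP with an SD of 0.26.

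**The concern.** The quantity of interest is each participant's Visit 2 value minus their Visit 1 value, attributed to ketosis. If the energetic state of the heart depends on the fuel reaching it, and feeding changes that fuel, then a participant scanned before eating at one visit and after a meal at the other carries a meal difference inside the measured change. The protocol permits this.

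Two things are at stake. The first is precision: meal differences that vary at random between participants widen the SD of the change for every imaging outcome. The second is interpretability. All three groups take the supplement, and the baseline scan always comes first, so a visit effect unrelated to ketones would have nothing to show against. The blood results help only in part. Insulin, lipids and glucose reflect the last meal as well as two weeks of supplementation, and glucose is itself expected to fall with ketosis.

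**Working it through.** **1. What is and is not controlled.** The two visits share the same place, the same stated maximum duration and the same no-fast rule. Clock time, interval since the last meal and interval since the last drink are not fixed in the text. By contrast, section 8.1 does time the home finger-prick test: just before and 30 minutes after the third drink. The scans that carry the primary endpoint have no such control.

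**2. The plan's own figure.** Inputs from section 10: target change 0.18 (one third of 2.07 − 1.54 = 0.53, i.e. 0.177), SD 0.26, two-sided 5% level, 25 per group, 90% power. Reading 0.26 as the SD of the within-person change and using a paired t-test:

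- noncentrality = (0.18 / 0.26) × √25 = 3.46 on 24 degrees of freedom
- power = 91.3% at 25 participants, and 90.1% at 24

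This reproduces the stated 25. The one-way analysis of variance named in section 10 does not: two groups of 25 give 66.9%. That mismatch is a separate matter. The paired reading is used below because it agrees with both the planned test and the stated size.

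**3. Random meal differences.** The documents give no meal effect, so the added SD *e*, on the scale of the change, is an assumption. New SD of change = √(0.26² + *e*²).

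| Added SD *e* | SD of change | Ratio to 0.26 | Power, n = 25 | Power, n = 30 |
|---|---|---|---|---|
| 0 | 0.260 | 1.00 | 91.3% | 95.6% |
| 0.05 | 0.265 | 1.02 | 90.3% | 94.9% |
| 0.10 | 0.279 | 1.07 | 87.3% | 92.8% |
| 0.15 | 0.300 | 1.15 | 82.0% | 88.8% |

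The ratio column is also the factor by which the confidence interval widens. The mean change is not biased in any of these rows.

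**4. A shift in one direction.** Suppose ketones had no effect, but meal state or timing moved PCr/ATP by a fixed amount *b* between visits. The chance of a significant paired test with 25 participants and an SD of 0.26 would be:

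- *b* = 0: 5%
- *b* = 0.02: 6.6%
- *b* = 0.05 (28% of the 0.18 target): 15.2%
- *b* = 0.09: 38.3%

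These show how sensitive the test would be, not that any shift exists. The document offers one possible route. Visit 1 lists consent, history, eligibility review and body measurements that Visit 2 does not, so the time from arrival to scan could differ if these come first. The order is not stated.

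**5. Perfusion and LVEF.** The same reasoning applies, but the protocol gives no SD for either, so no figure can be put on them.

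**The case against.** The strongest reply is that not fasting is a defensible choice and not a fault in a paired comparison. Section 4.1 says that fasting raises blood ketones, so unfasted scans help keep baseline ketones low and preserve the contrast. That stands, and the no-fast rule need not change.

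A reader might infer that the ketone effect is confounded with meals. The documents do not support this. Random mismatch costs precision only, and nothing shows that meal state or clock time moves the same way from Visit 1 to Visit 2.

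A reader might also treat 0.26 as the per-visit SD and use SD of change = 0.26 × √(2(1 − r)). If mismatch lowered the between-visit correlation r from 0.7 to 0.5, the SD would rise from 0.201 to 0.260, a 29% wider interval. Both correlations are assumed; neither is in the protocol. The supposed worst case, 0.26, is also the value at which 25 participants already give 91.3% power, so this is no loss against the plan.

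A third tempting reading is that the blood results can say nothing about meal effects. That is too strong. Ketones, glucose, insulin and lipids at both visits give a partial record of substrate state, and how they enter the analysis may properly be set out in a SAP, which was not available.

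Finally, two figures in section 8.1 could not be read, and neither the CRF nor the diary content is described, so some timing detail may sit there. That limits confidence. It does not remove the case for stating the requirement in section 8.1.

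**Conclusion.** The point holds as an avoidable loss of precision and a gap in what could be checked later, not as demonstrated bias. Its size is unknown. An added random SD of 0.05 to 0.10 would cost 1 to 4 percentage points of power at 25 participants, and 0.15 would cost about 9. With all 30 completing, power stays at 88.8% or above over that range. These figures assume that 0.26 is the SD of the change and that meal variation is independent of the other sources of variation.

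The case for acting rests on two further facts. A systematic visit effect could not be recognised in this design. A comparison of changes between groups would cancel only a shift of equal size in each group. And meal timing that is not recorded cannot be reliably recovered afterwards. The unfasted blood values cannot reliably separate meal from supplement without it.

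**What to change.** Keep the no-fast rule and add to section 8.1:

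- Schedule each participant's Visit 2 at about the same time of day as Visit 1, and in the same meal state: a similar light meal at a similar interval before the scan.
- Record the time of the last meal on the CRF at both visits.
- Record the time of the last ketone drink before the Visit 2 scan. Section 4.1 says blood ketones rise within 30 minutes of a drink, so this interval is a source of variation at least as close as the meal. The request is to record it only; it implies no change to the supplementation schedule.
- In section 8.2.1, label the insulin, lipid and glucose results as non-fasting.

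The cost is protocol wording, a few CRF fields and slightly less flexible scanner booking. No visit or procedure is added. If the figures in section 8.1 or the diary already cover any of this, a cross-reference in the text would do for that item.
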